#### **Table 5 Definition of TEAEs for Different Analyses**

An adverse event of special interest (AESI) is one of scientific and/or medical interest specific to understanding safety and action of the IP. The following are considered AESIs in this study:

- Anaphylaxis and serious hypersensitivity reactions
- Infusion-related reactions (IRR)
- Immune complex disease
- Cytopenia
- Serious and/or opportunistic infections, including Progressive Multifocal Leukoencephalopathy (PML).

The AESIs (investigator reported) will be summarized by Category and PT. The risk difference and corresponding 95% CI calculated by the Miettinen and Nurminen score method in cumulative incidences of AESIs by week 52 between inebilizumab and placebo groups may be presented as appropriate. In addition, the time to first instance of an AESI and duration of the AESI will be summarized by treatment group when appropriate.

In addition, following sponsor identified AESIs will also be summarized: IRR, anaphylaxis, serious hypersensitivity reactions, immune complex disease, cytopenia, serious infections, and opportunistic infections. The detailed definition of sponsor identified AESIs will be included in the statistical programming plan (SPP).

AEs will be coded to the corresponding system organ class (SOC) and preferred terms (PT) using the most recent version of the Medical Dictionary for Regulatory Activities (MedDRA). In addition, summary of AEs and SAEs by SOC and FDA Medical Query (FMQ) will also be provided for RCP and the combined period of RCP and OLP.

The number and percentage of subjects reporting TEAEs and TESAEs will be summarized for each treatment group by SOC and PT, by severity, and by relationship to the IP. If the same AE occurs multiple times within a particular subject, the highest severity and level of relationship observed will be reported.

TEAEs and TESAEs will be summarized as described in Table 6.

TEAEs per 100 Person-years for a specific reporting period will be calculated as

$$= 100 \times \frac{\text{Total number of TEAEs for specific reporting period}}{\text{Total Person years for specific reporting period}}$$

The person-year for while-on-treatment analyses will be defined as (Date of 6 months [183 Days] after the last RCP dose - 1st RCP dose date +1)/365.25. See Table 4 for the definition of person-years for other analyses.

Overall summary of TEAEs
TEAEs by SOC and PT
TEAEs with severity $\geq$ Grade 3 by SOC and PT
TEAEs resulting in permanent discontinuation of the IP by SOC and PT
TEAEs (≥5% in inebilizumab) by SOC and PT
TEAEs by SOC, PT and by highest severity
TEAEs by PT sorted by frequency in inebilizumab group
TEAEs by FMQ sorted by Frequency in Inebilizumab Group
TESAEs by SOC and PT
TESAEs by PT sorted by frequency in inebilizumab group
TESAEs by FMQ sorted by Frequency in Inebilizumab Group
TESAEs by Seriousness Criteria
TEAEs with Severity $\geq$ Grade 3 and/or TESAEs by SOC and PT
IP Related TEAEs by SOC, PT
IP Related TEAEs with Severity $\geq$ Grade 3 by SOC and PT
IP Related TEAEs by SOC, PT and by Highest Severity
IP Related TESAEs by SOC and PT
IP Related TEAEs with Severity $\geq$ Grade 3 and/or TESAEs by SOC and PT
AESI by Category, PT and by Highest Severity
Overview of TEAEs per 100 Person-years by SOC and PT
TEAEs per 100 Person-years by SOC and PT
Overview of TESAEs per 100 Person-years

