# **3** STATISTICAL METHODS

#### 3.1 General Considerations

The efficacy endpoints will be summarized at scheduled visits during RCP and OLP, respectively. For subjects in the OLP, the efficacy may also be summarized over the combined RCP and OLP to characterize the durability of the treatment effect, if applicable. And the summary over the combined RCP and OLP will be based on the subjects who received any dose of inebilizumab.

The safety endpoints will be summarized for the RCP, OLP, combined RCP and OLP, and SFP, respectively.

All efficacy analyses described below apply to the RCP unless stated otherwise.

The analyses with a treatment policy strategy will include all data captured during the 52week RCP, defined as the period after first IP administration at Visit 2 (Day 1) to the conclusion of the scheduled last RCP visit at Visit 15 (Week 52), inclusive, up to but not beyond Day 1 of the OLP.

As sensitivity analyses, the analyses applying the while-on-treatment strategy for safety endpoints will include all data captured while subjects are on treatment, defined as the period after randomization at Visit 2 and 6 months (183 days) after the last treatment during the RCP, inclusive.

All statistical calculations will be primarily performed using SAS® System Version 9.4 or higher. Tabular summaries will be presented by treatment arm. Categorical data will be summarized by the number and percentage of subjects in each category. Continuous variables will be summarized by descriptive statistics, including number of observations, mean, standard deviation, median, Q1, Q3, minimum, and maximum. Data listings will be sorted by treatment group and subject number.

Where appropriate, model-based estimates will be presented with their two-sided 95% confidence interval (CI) and p-values. Unless otherwise stated, nominal p-values will be reported and rounded to 4 decimal places.

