#### 3.4.3 Study Drug Exposure

Study drug exposure, which includes number of doses, dose amount and dose amount adjusted for weight (mg/kg) of the study drug, and durations of the study drug exposure, will be summarized for RCP, OLP, and Any Inebilizumab exposure by treatment group. In addition, treatment compliance will also be summarized for RCP.

The amount of study drug exposure: If entire dose was administered, the dose amount (mg) at a specific visit will be either 0 or 300 mg depending on what treatment the subject had received; if a subject received partial dose at a dosing visit, then the amount of study

drug at that dosing visit will be estimated based on the actual volume administered. For example, if a subject receives 175 mL (instead of the full 250 mL), the dose amount (mg) will be estimated as =  $300 \text{ mg} \times 175 \text{ mL} / 250 \text{ mL} = 210 \text{ mg}$  provided the subject received inebilizumab.

Treatment compliance for an individual subject = [Total number of doses received]/ [Total number of doses planned per protocol]  $\times 100\%$ .

The definition of duration of study drug exposure and person-years of exposure is outlined in Table 4.

RCP	OLP	Combined RCP and OLP (Any Inebilizumab Exposure)	
	Duration of study drug exposure		
Last RCP dose date $-1^{st}$ RCP dose date $+90^{a}$	Last OLP dose date $-1^{st}$ OLP dose date $+90^{a}$	Last inebilizumab dose date – 1 st inebilizumab dose date + 90 a	
Person-year definition for individual subject b			
$\begin{array}{c c} (\text{Date of last RCP day} - 1^{\text{st}} \text{ RCP dose} \\ \text{date} + 1)/365.25 \end{array} \\ \begin{array}{c c} (\text{Date of last OLP day} - 1^{\text{st}} \text{ OLP} \\ \text{dose date} + 1)/365.25 \end{array} \\ \begin{array}{c c} (\text{Date of last study day in RCP or} \\ \text{OLP} - 1^{\text{st}} \text{ inebilizumab dose date} + 1)/365.25 \end{array} \\ \end{array}$			
a Based on 5 half-lives (18 days) determined from previous late-stage clinical trials			
b Total person-years will be calculated as the sum of the person-years for individual subject			

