#### **3.6.1** Adverse Events

Adverse event and serious adverse event collection begins after the subject signs the informed consent document and continues until the end of study visit. AEs and SAEs collected during the RCP will be analyzed using a treatment policy strategy (which includes all data captured during the RCP), and a while-on-treatment strategy (which includes all data captured while subjects are on treatment). AEs and SAEs collected during the OLP, SFP and combined RCP and OLP, will be analyzed using a treatment policy strategy. For subjects who withdraw from the study, data collected up until the last visit will be included. Table 5 defines TEAEs for different analyses.

RCP (Treatment Policy)	RCP (While-on- treatment)	OLP	Combined RCP and OLP (Any Inebilizumab Analysis Set)	SFP
A TEAE is defined as any AE with onset date on or after the first RCP IP dose, and on or before the end of RCP.	A TEAE is defined as any AE with onset date on or after the first RCP IP dose, and on or before 6 months (183 Days) after the last RCP dose.	A TEAE is defined as any AE with onset date on or after first OLP IP dose and up to the end of OLP (prior to the SFP entry if a subject enrolled into SFP).	A TEAE is defined as any AE with onset date on or after the first inebilizumab dose (either RCP or OLP) and up to and including the day prior to the end of RCP (if a subject didn't enroll into OLP) or the end of OLP (i.e., the day prior to the SFP entry, if a subject rolled over to OLP).	TEAE is defined as any AE with onset date after the last IP dose during the study.

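### While-on-treatment person-years run to 183 days after the last RCP dose even when a subject has died, left the study or been lost, so these safety rates are understated

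*SAP*

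**What the plan says.** SAP 3.6.1 reports TEAEs and TESAEs per 100 person-years. For the RCP while-on-treatment version, the person-time rule is "The person-year for while-on-treatment analyses will be defined as (Date of 6 months [183 Days] after the last RCP dose", less the date of the first RCP dose, plus 1, over 365.25. The next sentence sends every other rate elsewhere: "See Table 4 for the definition of person-years for other analyses". In Table 4 (SAP 3.4.3) the RCP person-year ends at the "Date of last RCP day", that is, when the subject's RCP ends.

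On the event side, Table 5 counts while-on-treatment TEAEs with onset "on or before 6 months (183 Days) after the last RCP dose". SAP 3.1 and Protocol 9.1 define the period with the same six-month tail. The text of SAP 3.6.1 adds two limits. The data source for both RCP strategies is events from that period: "AEs and SAEs collected during the RCP will be analyzed using a treatment policy strategy", and likewise for while-on-treatment. For withdrawals: "For subjects who withdraw from the study, data collected up until the last visit will be included".

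SAP 3.1 gives the analysis its status: "As sensitivity analyses, the analyses applying the while-on-treatment strategy for safety endpoints will include all data captured while subjects are on treatment". Protocol 9.5.5 describes the rate as one per 100 person-years at risk.

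**The concern.** A rate is sound only if numerator and denominator cover the same observed time. Here the denominator runs for six months past the last dose whatever happens to the subject, while no event can be recorded after death or loss, and the SAP itself stops withdrawals at their last visit. The error has one direction: it adds person-time without the chance of an event, so it lowers the rate. It grows with the number of exits and depends on how soon after a dose they occur, so it need not be equal in the two arms. The analysis meant to show the event rate during active exposure would then be the one that dilutes it.

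**Working it through.** **Reference figure.** The plan states no person-year total to reproduce. The available internal comparison is a completer exactly on schedule: 183 + 183 - 1 + 1 = 366 days under the while-on-treatment formula, against 365 under the Table 4 RCP definition.

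**Inputs.** RCP doses on Days 1, 15 and 183 (Week 26), from SAP 2.2 and Protocol Table 4; tail of 183 days, from SAP 3.6.1. With Day 1 as first dose:

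- credited days = last dose day + 183
- observed days = min(exit day, last dose day + 183)

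**Single subjects whose adverse event observation ends on the exit day:**

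| Exit day | Last dose | Credited | Observed | Excess |
|---|---|---|---|---|
| 20 | Day 15 | 198 | 20 | 178 |
| 30 | Day 15 | 198 | 30 | 168 |
| 100 | Day 15 | 198 | 100 | 98 |
| 200 | Day 183 | 366 | 200 | 166 |
| 300 | Day 183 | 366 | 300 | 66 |

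A subject who stops IP but stays in the RCP for at least 183 days after the last dose has no excess.

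**Mean excess per leaver.** Take exit as equally likely on each of Days 1 to 364 (assumed). The mean excess is 176.5 days for exits on Days 1–14 and 99.5 for Days 15–182. For Days 183–364 it is 92.5 if all late leavers had the Week 26 dose and 0.66 if none did.

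- All dosed: (14×176.5 + 168×99.5 + 182×92.5)/364 = 98.96 days; mean observed 182.5.
- None dosed: (14×176.5 + 168×99.5 + 182×0.66)/364 = 53.04 days; mean observed 144.4.

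**Effect on the rate.** Let p be the proportion leaving observation early, assumed 3% to 20%. The low end matches the 97.0% RCP completion in Study 1155 (Protocol 2.1.5.3), a 28-week period in another disease. Let c be the completer's excess: 0 if the extra day is legitimate, 1 if it is not.

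- inflation = [p×excess + (1-p)×c] / [p×observed + (1-p)×(366-c)]
- understatement = 1 - 1/(1 + inflation)

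Example, p = 10%, all dosed, c = 1: (9.896 + 0.9)/(18.25 + 328.5) = 3.11%, an understatement of 3.02%.

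| p | None dosed, c = 0 | None dosed, c = 1 | All dosed, c = 0 | All dosed, c = 1 |
|---|---|---|---|---|
| 3% | 0.44% | 0.71% | 0.82% | 1.08% |
| 5% | 0.74% | 1.01% | 1.37% | 1.63% |
| 10% | 1.52% | 1.78% | 2.77% | 3.02% |
| 20% | 3.19% | 3.43% | 5.67% | 5.90% |

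Every cell treats each early leaver as unobserved after exit, so these are upper figures for a given p.

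**Between arms.** With equal true rates and all due doses given, 5% exit in one arm and 20% in the other produce a spurious rate ratio of (1-0.0163)/(1-0.0590) = 1.05. Small differences barely matter. One exit on Day 20 adds 178 days and four on Day 340 add 4×26 = 104; in 80 subjects (80×365 = 29,200 days) that is 0.61% against 0.36%.

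**Completers and the OLP.** Within the visit windows (Week 26 on Days 178–188, Week 52 on Days 358–372) the window end passes the Week 52 visit by 0 to 13 days. OLP Dose 1 may follow one day after that visit (Protocol 6.2.3.1), which is Day 366 on schedule, the last day of the while-on-treatment window. Protocol Table 4 allows the Week 26 dose to be delayed and states no maximum. A dose on Day 211, four weeks late (assumed), puts the window end at Day 394, 29 days past Day 365. SAP 3.1 caps the treatment-policy period at OLP Day 1 but puts no such cap on this one.

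**The case against.** The best reply is that numerator and denominator already share a window: Table 5, SAP 3.1 and Protocol 9.1 all run to six months after the last dose, and the formula follows them. Leaving the RCP also does not end adverse event collection. Protocol 8.3 records events until study exit, Protocol 6.2.3.1 collects those between the RCP and OLP at OLP Visit 1, and Protocol 6.2.4 follows subjects who do not enter the OLP for two years from the last infusion, with the first visit at Week 26.

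Much of this stands. A reader might infer that every early RCP leaver is over-credited, or that the completer's extra 1 to 13 days is plainly wrong. The documents do not support either reading. Both require the phrase about events gathered in the RCP to override the explicit Table 5 cell, and the withdrawal cut-off is written for subjects who leave the study, not for all who leave the RCP. Table 5 leaves this open: its SFP column also claims these events ("TEAE is defined as any AE with onset date after the last IP dose during the study") without saying whether they count in the while-on-treatment column too.

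The reply does not reach subjects who die, withdraw from the study or are lost. For them the windows agree on paper only.

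It is also fair that these are descriptive rates in a sensitivity analysis, and that treatment-policy rates with person-time ended at the last RCP day are reported beside them.

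**Conclusion.** The formula is wrong as written for subjects whose adverse event observation ends, through death, study withdrawal or loss to follow-up, within 183 days of the last RCP dose. It credits each of them unobserved time and understates the while-on-treatment TEAE and TESAE rates. Under the assumed 3% to 20% leaving observation uniformly over the year, the understatement is at most roughly 1% to 6%, and less to the extent that RCP leavers are followed in the safety follow-up period. The exit range and its timing are assumptions, because the documents give neither. For completers the excess is an error only if the limit to RCP events is taken to bind the Table 5 window. Separately, that window has no stop at OLP dosing and can run into it.

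It would be a mistake to read this as a bias in the trial's main safety or efficacy results. Subject counts and percentages, treatment-policy rates and all efficacy analyses are untouched.

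**What to change.** In the SAP 3.6.1 formula, end while-on-treatment person-time at the earliest of:

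- last RCP dose + 183 days;
- death;
- last adverse event contact or study exit;
- the day before OLP Dose 1.

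Apply the same end date to the RCP while-on-treatment column of Table 5, so that events and person-time cover the same observed days, and state there that events collected after RCP exit but before this date count. Capping at the last RCP day would be simpler, but it would discard events actually observed in follow-up within six months of the last dose, which Table 5 and Protocol 9.1 place inside the period.

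The cost is a line in the formula, a line in the Table 5 cell and one derived date in programming. No new data are needed. Reported rates will be slightly higher.

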#### Table 6 Type of TEAE Analyses by Period

TESAEs per 100 Person-years by SOC and PT

All deaths

Overall summary of TEAEs and summary of TEAEs by SOC and PT for treatment policy and while-on-treatment will be investigated when appropriate by age ( $< 65 \text{ vs} \ge 65$ ), sex (male vs female), region (US vs non-US; EU vs non-EU; Japan vs Non-Japan; and Asia vs non Asia), serum IgG4 concentrations at baseline ( $< \text{median vs} \ge \text{median}$ ),

racial/ethnic subgroups as needed for national/regional regulatory submissions, first or subsequent IgG4-RD manifestation (i.e., newly-diagnosed vs. recurrent), and by ADA status at any time during RCP including baseline (positive vs negative) if data allows.

Listings will be provided for all TEAEs and non-treatment emergent AEs.

#### 3.6.2 Clinical Laboratory Evaluation

Blood and urine samples will be collected for laboratory safety tests at baseline as well as throughout the study. Laboratory toxicities will be defined based on the National Cancer Institute's Common Terminology Criteria for Adverse Events (NCI CTCAE) version 5 for the tests with objective criteria and version 4 for the tests with subjective criteria. The international system of units will be used for all the lab data.

The analysis for the laboratory results is listed in Table 7.

Laboratory dataset	Planned Analysis
Hematology, Chemistry, and Coagulation	• Summary of worst post-baseline toxicity grade
	• Summary of at least 2-grade shift from the baseline to the worst post-baseline toxicity grade
	• Summary of shift from the baseline relative to the normal range
	• Summary of observed values, and changes and percent changes from the baseline
Urinalysis	• Summary of observed values, and changes and percent changes from the baseline
Serum Immunoglobulins	• Summary of observed values, changes and percent changes from the baseline

 Table 7 Laboratory Results Analysis

To evaluate the association between reduced Ig levels and infections/serious infections/opportunistic infections, those AEs will be summarized by the worst Ig Level during the combined RCP and OLP by the categories listed in Table 8.

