1 SYNOPSIS

Title	A Phase 3, Randomized, Double-blind, Multicenter, Placebo-Controlled Study of Inebilizumab Efficacy and Safety in IgG4 Related Disease
Short Title	MITIGATE
Phase	3
Study Design	Randomized, double-blind, placebo-controlled, parallel-cohort study
Rationale	There are currently no medicinal products approved for the treatment of immunoglobulin G4-related disease (IgG4-RD), a rare disease. The majority of cases follow a relapsing course that can lead to permanent tissue damage with attendant morbidity and potential mortality. Glucocorticoids (GCs) are widely and effectively used for acute treatment of initial disease activity and of recurrent episodes (flares), but GCs do not prevent recurrence of active disease during their taper or after their discontinuation. Moreover, GCs are associated with substantial toxicity. Thus, there is a high unmet medical need for therapies that prevent disease recurrence and limit GC exposure. The pathogenesis of IgG4-RD suggests that B-cell depletion may be an effective avenue for therapeutic intervention. An important role for B cells, particularly plasmablasts and plasma cells, in the pathogenesis of the disease appears likely. The anti-CD19 B cell-depleting activity of inebilizumab suggests that it may provide benefit as treatment for IgG4-RD. This study aims to define the efficacy and safety of inebilizumab for the prevention of flare of IgG4-RD.
Target Population	Male or female adults, who have reached the age of consent in the applicable region, who have recently active IgG4-RD (initial diagnosis or flare) that requires new or ongoing treatment, are at high risk of future flare (as evidenced by multi-organ disease involvement), and meet the 2019 American College of Rheumatology/European League Against Rheumatism (ACR/EULAR) IgG4-RD classification criteria.
Number of Subjects	Approximately 160 subjects will be randomized and dosed in a 1:1 ratio to 2 treatment groups; approximately 80 subjects to each treatment group. Enrollment may be increased to a maximum of 200 subjects total based on blinded event-rate analysis.
Length of Participation	Screening period: Up to 28 days Randomized-control period (RCP): 365 (± 7) days Optional open-label period (OLP): 1,095 (+ 10) days Safety Follow-Up period (SFUP) after investigational product (IP) discontinuation: 730 days Total maximum duration of study participation: 2,273 days

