2.1.4 Risk Assessment for Inebilizumab

The identified risks of inebilizumab are infusion-related reaction (IRR), arthralgia, neutropenia, and reduced immunoglobulin levels.

- Infusion reactions can include headache, nausea, somnolence, dyspnea, fever, myalgia, rash, or other symptoms. Most observed infusion reactions were mild to moderate in severity; however, rare, serious infusion reactions were observed. Potential risks associated with administration of inebilizumab are infection, redness, swelling, pain, and induration at the administration site. Prior to each IV infusion (inebilizumab or placebo) subjects will receive prophylaxis with IV methylprednisolone, oral diphenhydramine, and oral acetaminophen, or equivalent(s) to reduce the risk or severity of IRR.
- The proportion of subjects with arthralgia was numerically higher in the inebilizumab group than the placebo group during the RCP of Study CD-IA-MEDI-551-1155. There is

no known biological mechanism for a potentially higher rate of arthralgia with inebilizumab.

- Neutropenia was reported at low frequency and was generally transient. Neutropenia has been observed with other B cell depleting monoclonal antibodies (rituximab, ocrelizumab).
- Immunoglobulin levels have been observed to decrease with inebilizumab use, most significantly for IgM. Reduction in Ig levels has been observed with other B cell depleting monoclonal antibodies (rituximab, ocrelizumab) and may be a class effect.

Other important potential risks for inebilizumab are based on mechanism of action, nonclinical data, and clinical data. They include:

- Serious infections
- Progressive multifocal leukoencephalopathy (PML)
- Cytopenia
- Hypersensitivity (including anaphylaxis and serious skin reactions)
- Immune complex disease

The safety of use of inebilizumab during pregnancy is unknown; however, inebilizumab is a mAb, and immunoglobulins are known to cross the placental barrier. Transient peripheral B-cell depletion and lymphocytopenia have been reported in infants born to mothers exposed to other B cell-depleting antibodies during pregnancy. One uncomplicated pregnancy occurred in an inebilizumab-exposed subject who discontinued treatment. There were no birth defects in the baby. There are no data on the presence of inebilizumab in human breast milk, but lactating women should be advised not to breastfeed during treatment and for at least 6 months after the last dose.

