#### 3.3.4 Any Inebilizumab Analysis Set

The Any Inebilizumab Analysis Set includes all subjects who received any dose of inebilizumab during the study. Analyses with this analysis set will be based on the data collected on or after subjects receive the first administration of inebilizumab.

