#### **3.5.4 Exploratory Efficacy Endpoints and Analyses**

#### 3.6 Safety Analysis

Safety endpoints will be summarized separately for the RCP, OLP, SFP, and combined RCP and OLP. Safety data from the RCP and OLP will be presented based on the Safety Analysis Set and on the Open-label Analysis Set, respectively. Safety data from the combined RCP and OLP will be analyzed based on the Any Inebilizumab Analysis Set.

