#### **4 PLANNED ANALYSIS**

Two analyses are planned for this study. The primary analysis will be conducted after the last subject enrolled in the study has completed the RCP or discontinued prematurely. All the data collected by the date of the last visit during the RCP (or within 5 business days after the scheduled visit window for the last visit in case any data may be collected after the last scheduled visit, for example, image data etc.) will be included in the primary analysis. The final analysis will be performed after all subjects have completed the study or discontinued prematurely.

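### Grouping infections by each subject's worst immunoglobulin level over the whole RCP and OLP ignores time order and length of follow-up, and can bias the association in either direction

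*SAP*

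**What the plan says.** SAP section 3.6.2 gives the aim: "To evaluate the association between reduced Ig levels and infections/serious infections/opportunistic infections". The method is one line: "those AEs will be summarized by the worst Ig Level during the combined RCP and OLP", using categories in a Table 8 that is not in the public text.

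The surrounding rules fix the window:

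- SAP 3.6: "Safety data from the combined RCP and OLP will be analyzed based on the Any Inebilizumab Analysis Set".
- SAP 3.3.4: "Analyses with this analysis set will be based on the data collected on or after subjects receive the first administration of inebilizumab".
- SAP Table 5 closes the combined period for OLP subjects on the day before entry to safety follow-up.
- Protocol synopsis: "Randomized-control period (RCP): 365 (± 7) days" and "Optional open-label period (OLP): 1,095 (+ 10) days".
- SAP section 4: "The primary analysis will be conducted after the last subject enrolled in the study has completed the RCP or discontinued prematurely".

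The SAP does not say whether this table reports percentages of subjects or rates. Its general rule for categorical data (3.1), and its rule for TEAEs (3.6.1), is number and percentage. Person-year rates are listed in Table 6 for TEAEs and TESAEs, and not for this table.

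The background is in Protocol 2.1.4: "Immunoglobulin levels have been observed to decrease with inebilizumab use, most significantly for IgM". The same section lists reduced Ig as an identified risk and serious infection as an important potential risk.

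**The concern.** There are two separate problems.

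**Time order.** A subject is classed once, by the lowest Ig at any point in the window, and every infection in the window counts in that class. An infection early in treatment can be credited to a nadir reached years later.

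**Length of follow-up.** A subject observed for longer has more Ig samples, more time for Ig to fall, and more time to have an infection. A percentage-of-subjects comparison will then show more infection in the low class even if Ig plays no part. The opposite can also happen. Protocol 6.4.1 requires study drug to stop for sepsis, for listed opportunistic infections, and for Grade 3 or 4 infections. A subject who stops in the OLP moves to safety follow-up (Protocol Table 5, footnote h), so later and lower Ig values are never counted. Infected subjects then collect in the class that is not low, and a real association can be hidden.

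At stake is how the report describes the link between an identified risk and an important potential risk. No efficacy conclusion depends on it.

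**Working it through.** The documents give no figure for this analysis, so there is none to reproduce. The check asks what the planned grouping would show if infections were unrelated to Ig.

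**Maximum follow-up from first inebilizumab dose**

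- Inebilizumab arm, full OLP: (365 + 1,095) / 365.25 = 4.0 years, plus a gap of at most 38 days between periods.
- Placebo subjects who cross over: 1,095 / 365.25 = 3.0 years.
- Inebilizumab subjects who decline the OLP: 365 / 365.25 = 1.0 year.
- If the table is run at the primary analysis, OLP time is also staggered by date of enrolment.

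**Infection rates, from Study 1155 (Protocol 2.1.5.3), taking 197 days as the period**

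- Any infection, 37.9%: −ln(1 − 0.379) × 365.25 / 197 = 0.883 per person-year.
- Serious infection, 1.7%: −ln(1 − 0.017) × 365.25 / 197 = 0.032 per person-year.

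**Assumptions that are not in the documents.** Log-Ig declines linearly by 0.05, 0.10 or 0.15 per year on average (SD of slopes 0.05, SD of starting values 0.25, visit noise SD 0.08). Low means more than 0.40 log units below the mean starting value. Ig is measured at clinic visits. Infections follow a Poisson process independent of Ig. Each scenario had 400,000 simulated subjects.

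**Results under no effect, low versus not low by worst Ig (ranges over the three slopes)**

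| Follow-up | Odds ratio, any infection | Odds ratio, serious infection | Rate ratio per person-year |
|---|---|---|---|
| Equal, 4 years | 0.98 to 1.04 (both outcomes) | (see left) | 0.97 to 1.01 |
| 4 v 3 years by arm | 1.09 to 1.17 | 1.03 to 1.07 | 0.97 to 1.01 |
| About 10% dropout per year, or staggered data cut | 1.53 to 3.33 | 1.15 to 1.47 | 0.97 to 1.01 |
| 4 v 3 years, dropout, 30% of serious infections end the window | – | 0.93 to 0.97 | 0.68 to 0.85 (serious) |

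The 0.97 to 1.01 range covers the first three rows together.

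One scenario shows the mechanism. With slope −0.10 and 10% dropout per year, mean follow-up is 3.29 years in the low class and 2.67 in the other. Any infection occurs in 91.8% v 82.2%, and the odds ratio is (0.918 / 0.082) / (0.822 / 0.178) = 2.4. The ratio of percentages is only 91.8 / 82.2 = 1.12, because most subjects have an infection. For serious infection it is 9.9% v 8.1%, odds ratio (0.099 / 0.901) / (0.081 / 0.919) = 1.25.

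If every serious infection ended the window, the serious-infection odds ratio would be 0.25 to 0.54. That is an outer bound, because subjects who stop drug in the RCP stay in it to Week 52.

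**Time order.** Without infection-triggered stopping, 30% to 50% of infections in the low class came before that subject's first low value. With a constant infection rate, the same fraction f of that class's person-time is also before the fall. If low Ig truly multiplied the rate by R, the class would show f + (1 − f)R per person-year, which is less than R whenever R > 1. A real effect would be diluted.

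**The alternative.** Counting events and person-time as low only from the first low value gave null rate ratios of 0.98 to 1.01 in every scenario, including those in which the worst-level grouping was biased.

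**The case against.** A reader might infer that assigning infections to later Ig values is enough to manufacture an association. It is not. With equal follow-up the null odds ratio is about 1.0, although up to half of the low-class infections precede the first low value. A false positive also needs unequal follow-up and a percentage summary. The documents establish the first. The second is the SAP's default but is not stated for this table. Person-years for the combined period are defined in SAP Table 4 and could be used; they would remove the upward bias. They would not remove the downward one, because infections can end the window.

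It is also fair to say that this is a descriptive table with no test or decision rule, and that AEs are listed in full, so later exploration remains open. Table 8 and other parts of the SAP are not public, so one cannot say that this is the only analysis linking Ig to infection. Table 8 is cited for the categories, however, and would not by itself alter the explicit worst-level rule.

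Finally, the sizes depend on assumed Ig behaviour. The fall in Study 1155 was largest for IgM, while IgG below the lower limit of normal was less common on inebilizumab than on placebo at the end of its randomized period (3.8% v 9.4%). The distortion may therefore differ by Ig class. That limits the figures and leaves the direction of the argument unchanged.

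**Conclusion.** The concern holds in this form: the stated grouping takes no account of whether Ig fell before the infection or of how long each subject was observed, so it can bias the association in either direction. Under no effect, unequal follow-up with a percentage summary gives odds ratios from about 1.1 to above 2 for any infection, and about 1.03 to 1.47 for serious infection. If 30% of serious infections end the window, the serious-infection rate ratio is about 0.7 to 0.85. With equal follow-up the result is about 1.0. The infection rates come from Study 1155; Ig slope, variance, cut-off, dropout and the 30% are assumptions.

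The documents do not support going further and saying that the table must produce a false signal, or that it has no value as description. This is a cheap improvement.

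**What to change.** In SAP 3.6.2, classify each infection by the last Ig value before its onset, split each subject's person-time by current Ig category, and report infections per 100 person-years by current category, separately for any, serious and opportunistic infections. Keep the worst-level table as descriptive only, and state its denominator.

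The cost is a little more programming. It needs AE onset dates and the serial Ig values that SAP Table 7 already summarizes.

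There are two limits to accept. In OLP years 2 and 3 clinic visits are 26 weeks apart (Protocol Table 5), so the last Ig value can be about 6 months old. Serious infections will also be few. If all 160 subjects completed the OLP, person-time would be about 80 × 4 + 80 × 3 = 560 years, and at 0.032 per year about 18 serious infections would be spread over the Ig categories. Those rates should be shown with confidence intervals and read as descriptive.
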